1.0 Objectives

*The **primary objective** of this study is to determine the efficacy of the Life Walker versus a standard rollator walker and predicate assistive device on gait function in adults between 18 to 89 year of age and using a walker with or without back pain*

1.1 Hypothesis's:

Aim 1: Perform in-laboratory training on the Life Walker and testing to compare functional gait outcomes with the Life Walker compared to a conventional rollator and predicate assistive mobility device. *We expect that participants will be able to walk longer and will perform more efficiently on measures of gait function when using the Life Walker.*

Aim 2: Perform in-laboratory testing to compare self-reported pain with the Life Walker compared to a conventional rollator and predicate assistive mobility device. *We expect that participants will report less pain because they will have a more efficient and upright posture when using Life Walker.*

Aim 3: Perform in-laboratory testing to compare measures of quality of life with the Life Walker compared to a conventional rollator and predicate mobility device. *We expect that participants will report better outcomes on quality of life measures because they will experience better self-esteem due to better mobility when using Life Walker.*

2.0 Background

More than 6 Million people in the United States use assistive devices such as canes, crutches, or walker to move independently and to improve their balance. Over 1.5 million of these use walkers (Hamid Bateni) (H. Stephen Kaye). Independent movement is one of the most important factors to uphold quality of life for elderly or people with and patients with gait disorder, muscle weakness and musculoskeletal pain.

Mobility devices, especially rollators are used for improving the endurance, increasing the walking distance and the walking time (Zorica Suica). Due to the bilateral stabilization the base of support allows a bigger tolerance for the body mass center till losing balance. Up to 100% are load on the walker, depending on using which allows a decrease lower limb loading and compensate weakness and decrease fatigue. Wheeled Walker (rollator) need less effort for lifting and moving thereby decrease the energy cost up to 50%. (Ko CY; H. Stephen Kaye) Arm-rest can increase the comfort of the walkers and reduce the weight bearing on lower limbs and on hand and wrists additionally (Ko CY). The Life Walker is an ergonomically designed walker with forearm supports at a position which is meant to relieve pressure on important loading parts of a person's body

PROTOCOL TITLE: Life Walker vs. Conventional Rollator and Predicate Mobility Device

leading to better mobility. Thus the study aims at understanding the true utility of the walker.

3.0 Inclusion and Exclusion Criteria

3.1 We will recruit 30 subjects. Most subjects will be recruited through RIC recruitment flyers and from the RIC pain clinic.

Inclusion:

- Individuals using a walker with or without back pain for ambulation.
- Ages from 18 to 89 years old
- Medically stable for therapy

Exclusion

- Patient weight exceeds 300 lbs
- Patient height is below 5'0" or exceeds 6'3"
- Inactive, physically unfit to fit into the device.
- Cognitive deficits or visual impairment that would impair their ability to give informed consent or to follow simple instructions during the experiments.
- MMSE score below 17
- Pregnant women
- Co-morbidity that interferes with the study (e.g. stroke, pace maker placement, severe ischemia cardiac disease, etc.)

4.0 Study-Wide Number of Subjects

This study will enroll up to 30 older adults who use walkers as a primary mode of transportation, and 30 individuals who use a walker due to low back pain.

[figure not shown]
5.0 Study-Wide Recruitment Methods

This study will enroll up to 30 eligible subjects. RIC approved flyers will be posted at RIC in-patient, out-patient, day rehabilitation and fitness facilities, as well as pain clinic offices, providing contact information of study recruiters. Authorized research personnel will identify potential subjects from RIC's Cerner Information Systems. Patients will be

PROTOCOL TITLE: Life Walker vs. Conventional Rollator and Predicate Mobility Device

considered enrolled into the study after they have signed the Consent Form and HIPAA Authorization for Research.

6.0 Study Timelines: 1-2 days of training

PROTOCOL TITLE: Life Walker vs. Conventional Rollator and Predicate Mobility Device

Achievable benchmarks include: (1) recruitment of 30 subjects who use a walker and 30 subjects older adults who use a walker; (2) appropriate functional training of the LifeWalker Upright for all of the enrolled participants ; (3) completed clinical, performance outcome and self report measures for all of the of subjects.

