8.0 Procedures Involved

Participants will come to the laboratory for a screening and informed consent. Once written consent is obtained, participants will be screen for inclusion eligibility.

Screening/Baseline Procedures

- Informed Consent
- Medical history-Complete medical and surgical history, medications
- Demographics-Age, gender, race, ethnicity
- Review subject eligibility criteria
- Testing sessions will take place over the course of 1-32 days and include the following clinical objective outcome measures, subjective self-report measures and metabolic measures listed.

Overall Sessions:

- Session 1 will include, (i) Consent (ii) Some Self reported measures (baseline) and (iii) Indoor Gait assessment tests with or without metabolics (depending on equipment availability)
- Session 2 will include, (i) Outdoor ambulation, (ii) Indoor gait assessment with or without metabolics (depending on equipment availability), and (iii) Self reported measures
- Session 3 will include, any items that were not completed in session 1 or 2.

▪ Life Walker Upright Training Procedures

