8.1 Walker Training procedures

All participants will be trained on the use of the Life Walker and standard Rollator for a time of 15 min. After training all the testing will be begin.

8.2 Walker Testing procedures: *Experimental order of which walker is used first, second and third during the testing will be randomized using a random number generator.*

PROTOCOL TITLE: Life Walker vs. Conventional Rollator and Predicate Mobility Device

8.3 Overview: Participants will first complete a series of gait testing. Gait testing will include metabolic testing using the K4B2, load and grip testing using load sensors and upper extremity and spine muscle electromyography (EMG) testing. Participants will also be asked to be videotaped during their training sessions. After all the testing is complete, participants will be asked to complete a set of self-report questionnaires. During each device session, participant heart rate, blood pressure and blood oxygenation will be measured. All of these procedures will be repeated with each device.

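### Pre-test training is stated inconsistently and never covers the predicate device, and the participant's own walker is not a baseline item, so practice may differ by device and could not be examined

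*Protocol*

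**What the plan says.** Training appears in five places in the Protocol.

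- **Section 8.1**, the training procedure: "All participants will be trained on the use of the Life Walker and standard Rollator for a time of 15 min". It continues: "After training all the testing will be begin". The predicate device is not mentioned, and it is not said whether the 15 minutes apply to each device or to both together.
- **Section 6.0**, heading: "Study Timelines: 1-2 days of training". No device is named in this line.
- **Section 6.0**, second benchmark: "appropriate functional training of the LifeWalker Upright for all of the enrolled participants".
- **Section 1.1, Aim 1**: "Perform in-laboratory training on the Life Walker and testing to compare functional gait outcomes". No duration is given.
- **Section 8.0**, heading of the training part: "Life Walker Upright Training Procedures".

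Section 8.2 randomises which of three walkers is used first, second and third. The primary objective in 1.0 compares the Life Walker with both the rollator and the predicate device.

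On prior experience, section 3.0 admits "Individuals using a walker with or without back pain for ambulation" without specifying the kind of walker. The screening and baseline list in 8.0 covers consent, medical and surgical history, medications, demographics and eligibility. It has no item on the walker now in use or how long it has been used.

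**The concern.** Each participant is tested on every device, so the comparison is within person. That removes stable differences between people, but not differences in how practised a person is on one device relative to another. Such a difference belongs to the device and enters the paired contrast directly.

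There are three possible sources:

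- the training rule, which different parts of the Protocol describe differently in amount and in devices covered;
- the predicate device, for which no training is described;
- prior use, since someone who walks daily with a rollator brings experience to that device and none to a new one.

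At stake is how the device contrasts of the primary objective are read. A difference in walking distance or speed could partly reflect familiarity. If the habitual walker is never recorded, no later analysis can show how much of the contrast depends on it.

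**Working it through.** **1. The statements side by side.**

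| Place | Amount of training | Devices named |
|---|---|---|
| 8.1 | 15 min, per device or total not stated | Life Walker, standard rollator |
| 6.0 heading | 1-2 days | none |
| 6.0 benchmark | none | Life Walker |
| 1.1 Aim 1 | none | Life Walker |
| 8.0 heading | none | Life Walker |

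The amount conflicts between 8.1 and the 6.0 heading. The devices differ between 8.1 and the other three places that name one. The predicate device appears in no row. The session lists in 8.0 contain no training item, so they do not settle the matter.

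**2. The ambiguity within 8.1.** If the 15 minutes are per device, the Life Walker and the rollator each get 15 minutes. If they are shared equally, each gets 15 / 2 = 7.5 minutes. On either reading the predicate device gets 0 minutes under 8.1.

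**3. What random order does and does not do.** Write a result as person + period + device effect + practice on that device. With order randomised, period effects balance on average in the difference between two devices. What remains is

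expected paired difference = true device difference + (practice on device A − practice on device B).

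The bracket is the same whichever device comes first, so randomising order leaves it in place.

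**4. How prior use enters.** If a share p of participants are habitual rollator users with an advantage a on that device, the mean contrast moves by p × a. With assumed values p = 0.5 and a = 0.05 m/s, this is 0.5 × 0.05 = 0.025 m/s in the rollator's favour. The Protocol gives neither p nor a.

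**5. Illustration of the consequence.** The Protocol states no alpha, SD or effect size, so there is no planned figure to reproduce. Assume a two-sided 5% paired z-test, no true device difference, and a practice shift of d SDs of the paired difference. Then

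P(reject) = Φ(d√n − 1.96) + Φ(−d√n − 1.96).

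For d = 0.2 and n = 30: d√n = 0.2 × 5.477 = 1.095, so P = Φ(−0.865) + Φ(−3.055) = 19.5%.

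| Assumed d | n = 30 | n = 60 |
|---|---|---|
| 0 | 5% | 5% |
| 0.1 | 8.5% | 12.1% |
| 0.2 | 19.5% | 34.1% |
| 0.3 | 37.6% | 64.2% |
| 0.5 | 78.2% | 97.2% |

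The values 30 and 60 are used because section 16.0 gives both a total of 30 and two groups of 30. All values of d are assumed. The table shows that a modest shift would matter; it does not show that one exists.

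**The case against.** **Section 8.1 is probably the working rule.** Section 8.0 puts consent and indoor gait tests in session 1, plans two sessions with a third for unfinished items, and 15.2 pays accordingly. Fifteen minutes before testing fits this; one or two days does not. The 6.0 heading may simply mean the length of participation. This has force and makes 8.1 the likelier reading. It does not remove the inconsistency: the words in 6.0 refer to training, and 8.3 and 11.2 also speak of training sessions. Nor does it supply training on the predicate device.

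**A reader might infer that the Life Walker alone is trained for one to two days.** The Protocol does not say that. The 1-2 days line names no device, Aim 1 gives no duration, and nowhere is training restricted to the Life Walker. For the same reason no ratio of training times is supportable. Assuming 1 to 6 contact hours a day would give 60 to 720 minutes, or 60/15 = 4 to 720/15 = 48 times the amount in 8.1, but both the hours and their allocation to the Life Walker are assumptions.

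**A reader might also infer that neither a positive nor a null result could answer the efficacy question.** That does not follow. Under 8.1 both the Life Walker and the rollator are trained. If habitual use favours the rollator, a positive Life Walker result on that contrast would be conservative. Comparing a new device after brief training with a familiar one is also a legitimate practical question, provided the conclusion says so.

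**Analysis by habitual device normally belongs in the SAP, which is not at hand.** Agreed, and its absence from the Protocol is not a fault. Training and baseline data collection, however, are Protocol matters, and the SAP cannot use an item that was not collected.

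**Conclusion.** The point holds in a limited form. The Protocol is inconsistent on the amount of training and on which devices are trained, provides none on the predicate device, and does not list the participant's own walker at baseline. Practice may therefore be unequal across devices, and without the baseline item the part due to prior use could not be examined or adjusted for.

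The direction is not determined. Prior rollator use would favour the rollator; training weighted to the Life Walker would favour the Life Walker. The contrast most plainly exposed is Life Walker versus predicate, because 8.1 trains one of those devices and not the other. The text available does not describe the predicate device, so how familiar participants are with it is unknown.

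The size cannot be taken from the documents. The rejection rates above rest on assumed shifts and an assumed 5% paired test. This is a moderate matter, worth correcting because the correction is cheap and the missing baseline information may be hard to recover afterwards. It does not make the trial uninterpretable.

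**What to change.** 1. Reconcile 6.0, Aim 1, the training heading in 8.0 and 8.1 to a single training rule. It should give equal time on every tested device, including the predicate, and state whether the time is per device or in total. If the 6.0 heading is meant as length of participation, reword it.
2. Add the type of walker currently used and the duration of its use to the baseline list in 8.0.
3. Report the device contrasts by habitual walker type as a supportive analysis; the detail can sit in the SAP.
4. Word the conclusion as an effect after the stated training.

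The cost is Protocol wording, one form field and a little more training time for the predicate device. Estimates by habitual walker type will be less precise than the pooled contrast, so they should support it and not replace it. Equal training does not remove differences in prior experience; items 2 and 3 make those visible.

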8.0 Procedures Involved

Participants will come to the laboratory for a screening and informed consent. Once written consent is obtained, participants will be screen for inclusion eligibility.

Screening/Baseline Procedures

- Informed Consent
- Medical history-Complete medical and surgical history, medications
- Demographics-Age, gender, race, ethnicity
- Review subject eligibility criteria
- Testing sessions will take place over the course of 1-32 days and include the following clinical objective outcome measures, subjective self-report measures and metabolic measures listed.

Overall Sessions:

- Session 1 will include, (i) Consent (ii) Some Self reported measures (baseline) and (iii) Indoor Gait assessment tests with or without metabolics (depending on equipment availability)
- Session 2 will include, (i) Outdoor ambulation, (ii) Indoor gait assessment with or without metabolics (depending on equipment availability), and (iii) Self reported measures
- Session 3 will include, any items that were not completed in session 1 or 2.

▪ Life Walker Upright Training Procedures

8.1 Walker Training procedures

All participants will be trained on the use of the Life Walker and standard Rollator for a time of 15 min. After training all the testing will be begin.

8.2 Walker Testing procedures: *Experimental order of which walker is used first, second and third during the testing will be randomized using a random number generator.*

PROTOCOL TITLE: Life Walker vs. Conventional Rollator and Predicate Mobility Device

8.3 Overview: Participants will first complete a series of gait testing. Gait testing will include metabolic testing using the K4B2, load and grip testing using load sensors and upper extremity and spine muscle electromyography (EMG) testing. Participants will also be asked to be videotaped during their training sessions. After all the testing is complete, participants will be asked to complete a set of self-report questionnaires. During each device session, participant heart rate, blood pressure and blood oxygenation will be measured. All of these procedures will be repeated with each device.

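### Section 8.1 specifies pre-test training on two of the three walkers, leaving the Life Walker versus predicate comparison open to familiarity bias of unknown direction and size

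*Protocol*

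**What the plan says.** The primary objective (Protocol, 1.0) concerns the "efficacy of the Life Walker versus a standard rollator walker and predicate assistive device on gait function". All three aims repeat the two comparators, a rollator and a predicate device.

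On preparation, 8.1 reads: "All participants will be trained on the use of the Life Walker and standard Rollator for a time of 15 min". Testing follows directly. Section 8.2 randomises which walker comes first, second and third. Section 8.3 repeats the procedures with each device.

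Other places that bear on training or on prior use:

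- Section 6.0 sets a training benchmark that names one device: "appropriate functional training of the LifeWalker Upright for all of the enrolled participants".
- Section 11.1, on fall risk, provides for education in safe use of the device and for demonstration of safe use with assistive devices where necessary.
- Section 14.1 says who carries out training and to what standard, but names no device.
- Section 3.0 admits "Individuals using a walker with or without back pain for ambulation", and 4.0 describes one group as "older adults who use walkers as a primary mode of transportation". So every participant already uses a walker of some kind.
- The baseline list in 8.0 includes "Medical history-Complete medical and surgical history, medications" and "Demographics-Age, gender, race, ethnicity". It does not name the type of device habitually used or how long it has been used.
- Section 21.0 describes a single device, classed as a rolling walker. It does not identify the predicate.

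**The concern.** The predicate is tested like the other two walkers and serves as a comparator for the primary objective, yet 8.1 leaves it out of the training. Performance with a walker depends partly on how well the user knows it. Where preparation differs by device, the difference in results mixes what the device does with how familiar it is.

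At stake is whether the Life Walker versus predicate result can be read as a device effect. The exposure covers the six tests in 8.5: 10-metre walk, six-minute walk, dual-task walking, GAITRite, outdoor course and Dynamic Gait Index. The training step is a procedure that the protocol fixes and that happens before any data exist, so a statistical analysis plan cannot supply it later.

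**Working it through.** The protocol gives no figure to reproduce on this point, so the check is a comparison of its sections.

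**1. Count the devices.** Tested: 3 (8.2). With training specified: 2 (8.1). The predicate cannot be another name for the rollator, because 1.0 lists both and 8.2 counts a first, a second and a third walker.

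**2. Count the scheduled time.** Section 8.1 does not say whether the 15 minutes applies to each device or to both together.

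| Reading of 8.1 | Life Walker | Rollator | Predicate |
|---|---|---|---|
| Per device | 15 min | 15 min | none specified |
| Shared equally (assumed) | 15 / 2 = 7.5 min | 7.5 min | none specified |

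**3. Look for the missing step elsewhere.** Section 8.3 mentions filming during training sessions, and its closing sentence repeats procedures with each device. It is an overview of testing, however, and sets no training content or duration. Section 11.1 is a safety provision that is conditional and untimed. The benchmark in 6.0 names only the Life Walker, and 14.1 names no device. None of these gives training on the predicate that matches 8.1.

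**4. Ask whether randomised order repairs it.** Write the expected Life Walker minus predicate difference as

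D = δ + (f_L − f_P) + o,

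where δ is the device effect, f_L and f_P are the contributions of familiarity with each device, and o is the effect of test order. Randomising the order is aimed at o, since each device can fall in any position. It leaves f_L − f_P untouched, because that term goes with the device in every position.

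**5. Ask whether analysis repairs it.** If 8.1 is followed as written, the specified training on the predicate is absent for every participant. The data then hold no contrast between trained and untrained use of the predicate, and the effect of the missing step cannot be estimated or adjusted for. Prior familiarity may vary between participants and could be examined, but only if it is recorded, and 8.0 does not list it.

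**6. Work out the sign of f_L − f_P.**

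- *Study-supplied predicate, new to participants:* some training on the Life Walker against none specified on the predicate. The term may favour the Life Walker.
- *Participant's own walker as predicate:* 7.5 or 15 minutes on the Life Walker against habitual use. The term may favour the predicate.

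The text shown does not say which case applies.

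**7. Scope.** The Life Walker and the rollator are both named in 8.1, so the comparison between them is not affected by this omission. That leaves 1 of the 2 comparisons in the primary objective.

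**The case against.** The strongest reply is that the omission may be deliberate. If the predicate is the participant's own walker, training on it is unnecessary and 8.1 lacks only a definition. That definition may lie in material not shown: a figure is missing in 4.0, some text was removed, and the visible numbering passes from 6.0 to 8.0. This stands as a limit on what can be claimed about bias. It does not change the wording of 8.1, which trains on two of three devices and gives no reason.

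A second reply is that 8.1 may not be the whole story. Section 8.3 speaks of training sessions in the plural, and 11.1 speaks of assistive devices in the plural, a term close to the one 1.0 uses for the predicate. A reader might infer from 8.1 that participants meet the predicate with no preparation at all. The documents do not support that reading, since some safe-use instruction may reach it. Nor do these two places supply matched training.

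Third, participants practise during testing. Each device is walked six times in the 10-metre test and six times on the GAITRite, 12 recorded walks in all. This may narrow a gap in familiarity. The protocol does not fix the sequence of tests, so the mitigation is partial and cannot be sized.

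Finally, walker use is an inclusion criterion, so current use is checked at entry. That is fair, but the check does not yield the type of device or the length of use.

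**Conclusion.** The point holds in a limited form. As written, 8.1 gives unequal preparation for one of the two comparisons in the primary objective, and neither randomised order nor later analysis removes a training difference that every participant shares. It should be corrected before data collection.

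A reader might go further and infer that the design is tilted in favour of the Life Walker. The documents do not support this. It would require the predicate to be a device new to participants, which is nowhere stated; if it is their own walker, the tilt may run the other way. Familiarity bias is possible, not shown. Its direction depends on the unstated identity of the predicate, and its size cannot be derived from the protocol.

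The conclusion rests on two things: that the visible sections are the operative ones, and that familiarity can affect performance on the tests in 8.5. The 7.5-minute figure assumes an equal split of the 15 minutes.

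**What to change.** 1. Identify the predicate in 1.0 and 8.1, either as one named device or as the participant's own walker.
2. Amend 8.1 so that every participant receives the same familiarisation on the Life Walker, the standard rollator and the predicate before testing, and state whether the 15 minutes is per device.
3. If the predicate is the participant's own walker and is to stay exempt, say so in 8.1 with the reason. Add habitual device type and length of use to the baseline list in 8.0, and interpret that comparison as a new device against a habitual one.

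Cost: a short amendment. Under step 2, about 7.5 more minutes per participant if the 15 minutes is shared between two devices, or 15 if it is per device. Under step 3, two baseline items and no added training time. The price of step 3 is a narrower conclusion, because habit then remains part of the comparison.
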